1. PROTOCOL SUMMARY

1.1. Synopsis

Study Title:	A Window of Opportunity Study to Characterize the Safety, Dose Tolerance, Pharmacokinetics, and Pharmacodynamics of CPX-POM in Patients with Newly Diagnosed or Recurrent Bladder Tumors
IND Number:	132545
Study Centers Planned:	One center in the United States
Objectives:	
The primary objective is:
 
To characterize the safety and dose tolerance of CPX-POM administered as 900 mg/m² by 20-minute intravenous (IV) infusion once daily for 5 days to patients with newly diagnosed or recurrent bladder tumors who will be scheduled to undergo transurethral resection of a bladder tumor (TURBT) 
The secondary objectives are:
 
To determine the number of patients with treatment-related adverse events (AEs)To elucidate mechanisms of CPX-POM action on bladder tumor tissues employing an unbiased approach, using ribonucleic acid sequencing (whole transcriptome shotgun sequencing, RNA-seq) and chromatin immunoprecipitation-DNA sequencing (ChIP-seq)To determine the change in bladder tumor tissue cell proliferation, Notch and Wnt cell signaling pathways, as well as bladder tumor tissue CD8+ tumor-infiltrating lymphocytes (TIL) via immunohistochemistryTo determine bladder tumor tissue-to-plasma and tissue-to-urine ciclopirox (CPX) concentration ratios

Study Design:	
This will be an open-label study to determine the safety, dose tolerance, pharmacokinetics, and pharmacodynamics of CPX-POM in patients with newly diagnosed or recurrent, untreated or intravesical treatment completed >6 months before the current diagnosis, resectable tumors. Approximately 12 patients will be enrolled and treated with 900 mg/m² CPX-POM administered IV over 20 minutes once per day for 5 days followed by TURBT on Day 5 after the fifth dose. TURBT will be performed 2 to 6 hours following drug administration on Day 5.
 
Pretreatment bladder tumor tissues will be obtained at the time of in-office cystoscopy by cold cup biopsy within 4 weeks of TURBT. Posttreatment bladder tumor tissues will be obtained at TURBT. Bladder tumor tissues will undergo pathological evaluation at each site.
 
Prior to administration of the first CPX-POM dose on Day 1, pre-dose blood (plasma) and urine (clean catch) samples will be collected. At the time of TURBT on Day 5, one 3-mL blood (plasma) sample and a urine specimen will be collected for measurement of CPX-POM concentrations.
 
Patients will be followed for at least 30 days after the last dose of CPX-POM for safety.

Number of Patients Planned:	Approximately 12 patients will be enrolled.
Target Population:	The target population for this study is patients with newly diagnosed bladder tumors, inclusive of recurrent disease, who are treatment-naïve or had treatment completed >6 months before screening, and will be scheduled to undergo TURBT
Duration of Study:	Patients will be in this study for approximately 9 weeks: up to a 28-day screening period, a 5-day treatment period, and a 30-day follow-up period.
Diagnosis and Main Eligibility Criteria:	Patients eligible for enrollment will be adults who are likely to have a new bladder tumor based on clinical presentation or who are at high risk for tumor recurrence based on previous history, which is subsequently confirmed cystoscopically and will be scheduled to undergo TURBT. Patients must be treatment-naïve or had treatment completed >6 months before screening, and have an estimated glomerular filtration rate (eGFR) >30 mL/min/1.73 m ² .
Test Product, Dose, and Mode of Administration:	Patients will begin treatment with CPX-POM on a Monday, 4 days before the date of scheduled TURBT on a Friday. Patients will receive CPX-POM 900 mg/m ² by 20-minute IV infusion once daily for 5 days followed by TURBT after the last dose on Day 5.
Reference Therapy, Dose, and Mode of Administration:	Not applicable.
Criteria for Evaluation:	
Safety and Dose Tolerance:
 
Safety and tolerability will be based on an assessment of AEs, physical examinations, vital signs, electrocardiograms (ECGs), clinical laboratory tests, ophthalmologic assessments, and concomitant medications.

Pharmacokinetics and Pharmacodynamics

Bladder cancer tissue will be obtained at the time of in-office biopsy during cystoscopy and at TURBT and will be evaluated by the departments of pathology at the clinical sites. Bladder tumor tissues will be analyzed using RNA-seq and ChIP-seq to elucidate mechanisms of CPX-POM action. To determine the change in bladder tumor tissue cell proliferation, Notch and Wnt cell signaling pathways, as well as bladder tumor tissue CD8+ TILs, immunohistochemistry will be performed on paraffin-embedded slides. Concentrations of CPX-POM, CPX, and ciclopirox glucuronide (CPX-G) in urine, plasma, and tumor tissue collected at the time of TURBT on Days 1 and 5 will be determined by Good Laboratory Practices (GLP)-validated liquid chromatography-tandem mass spectrometry (LC-MS/MS) methods. Urine β -glucuronidase activity will be determined in the urine specimens collected on Days 1 and 5 by enzyme linked immunosorbent assay (ELISA).

**Statistical
Methods:**

Safety and Dose Tolerance:

Safety data will be presented in by-patient listings. Categorical safety endpoints will be summarized by frequency of events/abnormalities for each dose group and overall. Continuous safety endpoints will be summarized using descriptive statistics (number of subjects [n], mean, standard deviation, median, first quartile [Q1], third quartile [Q3], minimum, maximum) for each dose group and overall.

Pharmacokinetics and Pharmacodynamics:

By-patient listings of the results of bladder tumor tissues RNA-seq and ChIP-seq analyses will be provided. By-patient listings of immunohistochemical analysis of pre-treatment and TURBT bladder tumor tissues will be provided.

By-patient listings of concentrations of CPX in tumor, plasma, and urine will be provided. Bladder tumor tissue-to-plasma and tissue-to-urine CPX concentration ratios will be presented for each patient.

By-patient listings of urine β -glucuronidase activity will be provided.

This study will be conducted in accordance with the guidelines of current GCPs including archiving of essential documents.

1.2. Study Diagram

The study design is illustrated in [Figure 1](#).

1.3. Schedule of Assessments

The schedule of assessments is shown in [Table 1](#).

Table 1. Schedule of Assessments

Study Procedure	Screening Period	Treatment Period					Follow-up Period / ET ¹
	Study Days: D -28 to D -1	D1	D2	D3	D4	D5	D35
Study Visits:	V1	V2	V3	V4	V5	V6	V7
Informed consent	X						
Cystoscopy / cold cup biopsy	X						
Inclusion/exclusion criteria	X	X					
ECOG Performance Status	X						
Medical history	X						
Pregnancy test ²	X	X					X
MUGA or ECHO	X						
Chest X-ray or CT scan	X						
Obtain tumor tissue sample ³	X					X	
Hematology ⁴	X	X		X		X	X
Clinical chemistry ⁵	X	X		X		X	X
Urinalysis ⁶	X	X		X			X
Full physical exam ⁷	X						X
Assess for physical symptoms/toxicities ⁷		X	X	X	X	X	
Vital signs ⁸	X	X	X	X	X	X	X
ECG ⁹	X	X				X	X
Adverse events ¹⁰	X	X	X	X	X	X	X
Concomitant medications ¹¹	X	X	X	X	X	X	X
PK blood sample ¹²		X				X	
PK urine sample ¹³		X				X	
Body surface area ¹⁴		X					
CPX-POM infusions ¹⁵		X	X	X	X	X	
TURBT ¹⁶						X	

Abbreviations: AE = adverse event; ALT = alanine aminotransferase; aPTT = activated partial thromboplastin time; AST = aspartate aminotransferase; BSA = body surface area; BUN = blood urea nitrogen; CPX-G = ciclopirox glucuronide; CPX-POM = ciclopirox phosphoryloxymethyl ester; CT = computed tomography; D = day; ECG = electrocardiogram; ECOG = Eastern Cooperative Oncology Group; EDTA = ethylenediamine tetraacetic acid; eGFR = estimated glomerular filtration rate; ELISA = enzyme linked immunosorbent assay; ET = early termination; GGT = gamma glutamyl transferase; IV = intravenous; LC-MS/MS = liquid chromatography-tandem mass spectrometry; MUGA = multi-gated acquisition; PD = pharmacodynamic; PK = pharmacokinetic; PT = prothrombin time; QTc = corrected QT interval; RBC = red blood cell; RC = radical cystectomy; SAE = serious adverse event; TURBT = transurethral resection of a bladder tumor; V = visit; WBC = white blood cell.

1. Safety follow-up assessments will be performed within 30 days (± 3 days) after the last dose of CPX-POM. Or, in the event that a patient discontinues from the study prematurely, the site will make every effort to perform the assessments listed for this study visit.
2. Pregnancy tests will be required only for women of childbearing potential at Screening and before dosing on Day 1. Urine or serum pregnancy tests are acceptable.
3. Pre-treatment bladder tumor tissue sample will be obtained during in-office cystoscopy by cold cup biopsy within 4 weeks of TURBT. Post-treatment bladder tissue sample will be obtained at surgical resection (TURBT) on Day 5.
4. Hematology will include measurement of hemoglobin, hematocrit, platelets, RBC, reticulocytes, and WBC with differential.
5. Clinical chemistry will include measurement of potassium, sodium, chloride, glucose, BUN, creatinine, creatinine clearance, ALT, AST, GGT, alkaline phosphatase; indirect bilirubin, direct bilirubin, total bilirubin, total protein, albumin, calcium, bicarbonate, magnesium, phosphate, lipase, and amylase.
6. Urinalysis will include color, turbidity, pH, specific gravity, glucose, ketones, nitrites, bilirubin, urobilirubin, protein, RBCs, WBCs, epithelial cells, casts, crystals, and bacteria, and eGFR at Screening only.
7. A full physical examination will be conducted at Screening and at Visit 7/Follow-up. At each other study visit, patients will be assessed for continued dosing and any possible physical symptoms/toxicities and a physical examination may be performed, if indicated. Body weight should be measured at each study visit. Height should be measured at Screening.
8. Vital signs will be measured before any blood draws scheduled for the same time point. Vital signs will include blood pressure, respiratory rate, pulse, oxygen saturation, and temperature.
9. At Screening, 12-lead ECGs will be performed in triplicate, with each measurement separated by 2 minutes. The average of the 3 screening ECGs will be used to calculate QTc interval to determine study eligibility. Thereafter, single 12-lead ECGs will be performed for all patients prior to drug administration on Days 1 and 5 and at the Final Study visit.
10. All AEs and SAEs will be collected from the signing of the informed consent form through the time of TURBT. Starting at TURBT, only AEs related to CPX-POM treatment should be recorded; AEs related to the TURBT will not need to be recorded.
11. All concomitant medications will be recorded from the time of Screening up to the time of TURBT. Starting at TURBT, only medications associated with an AE related to CPX-POM treatment need to be recorded; routine medications and medications associated with the TURBT procedure do not need to be recorded.
12. Single blood (plasma) samples will be taken on Day 1 prior to CPX-POM administration and on Day 5 at the time of TURBT. Concentrations of CPX-POM, CPX, and CPX-G will be determined in these samples by LC-MS/MS. The date and time of sample collection will be recorded.

13. A clean catch urine sample will be collected on Day 1 prior to CPX-POM administration. A second urine specimen will be collected on Day 5 at the time of TURBT. Concentrations CPX-POM, CPX, and CPX-G will be determined in these samples by LC-MS/MS. Urine β -glucuronidase activity will also be determined in these samples by ELISA.
14. BSA will be calculated by the site personnel using the Dubois method of calculation using screening (Visit 1) height and baseline (Visits 2) weight measurements.
15. CPX-POM infusions will be administered as 900 mg/m² 20-minute IV infusion once daily for 5 days. Patients will be observed for at least 1 hour after completion of each infusion of CPX-POM.
16. TURBT will be performed within 2 to 6 hours after the last dose of CPX-POM has been administered on Day 5.

GLOSSARY OF ABBREVIATIONS AND DEFINITION OF TERMS

AE	adverse event
ALT	alanine aminotransferase
ANC	absolute neutrophil count
AUC	area under the concentration-time curve
BSA	body surface area
ChIP-seq	chromatin immunoprecipitation-DNA sequencing
CNS	central nervous system
CPX	ciclopirox
CPX-G	ciclopirox glucuronide
CPX-O	ciclopirox olamine
CPX-POM	ciclopirox phosphoryloxymethyl ester (ciclopirox prodrug)
CRF	case report form(s)
CRO	contract research organization
CTCAE	Common Terminology Criteria for Adverse Events
ECG	electrocardiogram
ECHO	echocardiography
ECOG	Eastern Cooperative Oncology Group
eGFR	estimated glomerular filtration rate
FDA	(United States) Food and Drug Administration
GCP	Good Clinical Practice
GLP	Good Laboratory Practices
IB	Investigator's Brochure
ICF	informed consent form
ICH	International Council on Harmonisation
IRB	institutional review board
IV	intravenous
MIBC	muscle invasive bladder cancer
MTD	maximum tolerated dose
MUGA	multi-gated acquisition
n	number of subjects
NCI	National Cancer Institute
NMIBC	nonmuscle invasive bladder cancer
NOAEL	no observed adverse effect level

NYHA	New York Heart Association
PD	pharmacodynamic(s)
PK	pharmacokinetic(s)
QTc	corrected QT interval
QTcF	QT interval corrected using Fridericia's formula
RC	radical cystectomy
RNA	ribonucleic acid
RNA-seq	RNA-sequencing or whole transcriptome shotgun sequencing (use of next-generation sequencing to reveal the presence and quantity of RNA in a biological sample)
RP2D	recommended phase 2 dose
SAE	serious adverse event
SOC	system organ class
TIL	tumor infiltrating lymphocyte
TURBT	transurethral resection of a bladder tumor
ULN	upper limit of the normal range

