8. STUDY ASSESSMENTS

8.1. Safety Assessments

8.1.1. Adverse Events and Serious Adverse Events

8.1.1.1. Definitions

Adverse Event

An AE is any untoward medical occurrence in a clinical investigation subject administered a medicinal product and which does not necessarily have a causal relationship with this treatment. An AE can therefore be any unfavorable and unintended sign, symptom, or disease temporally associated with the use of a medicinal product, whether or not considered related to the medicinal product.

AEs also include the following:

- Pre- or post-treatment complications that occur as a result of protocol mandated procedure (e.g., such as venipuncture, biopsy) during or after Screening (before the administration of study investigational medicinal product).
- Any pre-existing condition that increases in severity, or changes in nature during or as a consequence of the study investigational medicinal product phase of a human clinical trial, will also be considered an AE.
- Complications and termination of pregnancy (see Section [8.1.2](#) for additional information)
- All AEs that occur from the study screening visit onwards and throughout the duration of the study, including the follow-up off study medication period should be recorded as an AE.

An AE does not include the following:

- Medical or surgical procedures (e.g., surgery, endoscopy, tooth extraction, transfusion) performed; the condition that leads to the procedure is an AE.
- Pre-existing diseases or conditions or laboratory abnormalities present or detected before the screening visit that do not worsen.
- If progression of underlying malignancy is clearly consistent with the suspected progression of the underlying cancer as defined by the Response Evaluation Criteria in Solid Tumors (RECIST) 1.1, or with clinical symptoms (clinical progression), it should not be reported as an AE/SAE. Similarly, hospitalization due exclusively to the progression of underlying malignancy should NOT be reported as an SAE.

- Situations where an untoward medical occurrence has not occurred (e.g., hospitalization for elective surgery, social and/or convenience admissions).
- Any medical condition or clinically significant laboratory abnormality with an onset date before the consent form is signed and not related to a protocol-associated procedure is not an AE. It is considered to be pre-existing and should be documented on the medical history case report form (CRF).
- Uncomplicated pregnancy.

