- Other situations. Medical or scientific judgment should be exercised in deciding whether SAE reporting is appropriate in other situations such as important medical events that may not be immediately life-threatening or result in death or hospitalization but may jeopardize the patient or may require medical or surgical intervention to prevent one of the other outcomes listed in the above definition. These events should usually be considered serious. Examples of important medical events include invasive or malignant cancers, intensive treatment in an emergency room or at home for allergic bronchospasm, blood dyscrasias or convulsions that do not result in hospitalization, or development of drug dependency or drug abuse.

8.1.1.2. Time Period and Frequency for Collecting Adverse Event and Serious Adverse Event Information

All AEs and SAEs will be collected from the signing of the informed consent form (ICF) through the Follow-up visit (28 +/- 5 days after the last dose of study drug).

Medical occurrences that begin before the start of study intervention but after obtaining informed consent will be recorded on the Medical History/Current Medical Conditions section of the CRF not the AE section.

Investigators are not obligated to actively seek AE or SAE after conclusion of the study participation. However, if the investigator learns of any SAE, including a death, at any time after a patient has been discharged from the study, and he/she considers the event to be reasonably related to the study intervention or study participation, the investigator must promptly notify the Sponsor.

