8.1.1.5. Reporting Procedures

When an AE/SAE occurs, it is the responsibility of the investigator to review all documentation (e.g., hospital progress notes, laboratory reports, and diagnostics reports) related to the event. The investigator will then record all relevant AE/SAE information in the CRF.

It is not acceptable for the investigator to send photocopies of the patient's medical records in lieu of completion of the AE/SAE CRF page. There may be instances when copies of medical records for certain cases are requested by CicloMed or its designee. In this case, all patient identifiers, with the exception of the patient number, will be redacted on the copies of the medical records before submission.

The investigator will attempt to establish a diagnosis of the event based on signs, symptoms, and/or other clinical information. Whenever possible, the diagnosis (not the individual signs/symptoms) will be documented as the AE/SAE.

All SAEs will be recorded and reported to the Sponsor or their designee within 24 hours from the time any site team member is made aware of the event. The investigator will submit any updated SAE data to the Sponsor within 24 hours of it being available. If any part of the source providing details of the event is not available, the Investigator will submit the SAE with as much information as he/she has at the time of the reporting requirements.

Contacts and procedures for SAE reporting can be found in the Study Procedures Manual.

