8.1.3.7. Clinical Laboratory Assessments

All protocol-required laboratory assessments, including hematology (including complete blood count), clinical chemistry (including comprehensive metabolic panel), and urinalysis must be conducted in accordance with the Study Procedures Manual and the Schedules of Assessments ([Table 1](#)).

Abnormal laboratory tests that are clinically significant should also be recorded as AEs on the CRF, or as medical history if noted during Screening.

A listing of clinical laboratory tests to be performed is provided in [Table 3](#).

Table 3. Listing of Required Screening and Safety Laboratory Parameters

Laboratory Assessments	Parameters		
Hematology (CBC with differential)	
 • Hemoglobin • Hematocrit • Platelet count • RBC count • Reticulocytes 	WBC Count with Differential	
 • Neutrophils • Lymphocytes • Monocytes • Eosinophils • Basophils
Clinical Chemistry (including CMP)	
 • Potassium • Sodium • Chloride • Glucose • BUN • Creatinine • Creatinine clearance 	
 • ALT • AST • GGT • Alkaline phosphatase • Direct bilirubin • Indirect bilirubin • Total bilirubin 	
 • Total protein • Albumin • Calcium • Bicarbonate • Magnesium • Phosphate • Lipase • Amylase
Routine Urinalysis	
 • Color • Turbidity • pH • Specific gravity • Glucose • Ketones 	
 • Nitrites • Bilirubin • Urobilirubin • Protein • RBCs • WBCs 	
 • Epithelial cells • Casts • Crystals • Bacteria • eGFR (Screening only)
Other	Serum or urine hCG pregnancy test (for women of child bearing potential)		

Abbreviations: ALT = alanine aminotransferase; aPTT = activated partial thromboplastin time; AST = aspartate aminotransferase; BUN = blood urea nitrogen; CBC = complete blood count; CMP = comprehensive metabolic panel; eGFR = estimated glomerular filtration rate; GGT = gamma glutamyltransferase; hCG = human chorionic gonadotropin; MCH = mean corpuscular hemoglobin; MCV = mean corpuscular volume; PT = prothrombin time; RBC = red blood cell; WBC = white blood cell.

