9.5.1. Adverse Events

Clinical and laboratory AEs will be coded using the Medical Dictionary for Regulatory Activities (MedDRA). SOC, High-Level Group Term (HLGT), High-Level Term (HLT), Preferred Term, and Lower-Level Term (LLT) will be attached to the clinical database.

AEs will be summarized on the basis of the date of onset for the event. A treatment-emergent AE will be defined as any AE that begins on or after the date of first dose of CPX-POM.

Summaries (number and percentage of patients) of treatment-emergent AEs (by SOC, and Preferred Term) will be provided by dose group/cohort and overall.

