### **9.4 Adverse Events**

All adverse event summaries will be restricted to Treatment Emergent Adverse Events (TEAE), which are defined as those AEs that occurred after first CPX-POM dosing and those existing AEs that worsened during the study. This will not include AEs that are due to the operative TURBT procedure. If it cannot be determined whether the AE is treatment emergent due to incomplete or missing data, then it will be considered treatment emergent. Verbatim terms will be mapped to preferred terms and system organ classes using the Medical Dictionary for Regulatory Activities (MedDRA) (version 23.1).

Summaries that are displayed by system organ class and preferred terms will be ordered by descending order of incidence of system organ class and preferred term within each system organ class. The following summaries will be provided:

- Overall summary of AEs
- TEAEs by system organ class and preferred term
- TEAEs by system organ class, preferred term, and highest intensity
- Related TEAEs by system organ class and preferred term
- Serious TEAEs by system organ class and preferred term
- Serious Related TEAEs by system organ class and preferred term
- TEAEs leading to study discontinuation by system organ class and preferred term
- TEAEs resulting in death

Related events will be any event having the causality field marked as “Related” or missing on the Adverse Event eCRF page. Intensity (Grade) of AEs will be based on the NCI Common Terminology Criteria for Adverse Events (CTCAE) (5.0).

All AEs will be provided in a listing.

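### The protocol gives two incompatible rules for recording adverse events after TURBT, so the all-cause TEAE tables may be all-cause only up to surgery

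*Protocol*

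**What the plan says.** Footnote 10 to Table 1 (Protocol 1.3) sets a cut-off at surgery. Its first sentence reads "All AEs and SAEs will be collected from the signing of the informed consent form through the time of TURBT", and its second "Starting at TURBT, only AEs related to CPX-POM treatment should be recorded; AEs related to the TURBT will not need to be recorded". TURBT takes place 2 to 6 hours after the fifth dose (footnote 16).

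Section 8 of the protocol has no such cut-off. Section 8.1.1.2 says "All AEs and SAEs will be collected from the signing of the informed consent form (ICF) through the Follow-up visit". Section 8.1.1.1 says that AEs from screening onward and "throughout the duration of the study, including the follow-up off study medication period should be recorded as an AE". On serious events, 8.1.1.5 says "All SAEs will be recorded and reported to the Sponsor or their designee within 24 hours". None of these sentences is limited by relatedness.

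The definitions used for analysis are not limited by relatedness either. Protocol 9.5.1: "A treatment-emergent AE will be defined as any AE that begins on or after the date of first dose of CPX-POM". SAP 9.4 restricts its summaries to TEAEs, "which are defined as those AEs that occurred after first CPX-POM dosing and those existing AEs that worsened during the study", and then removes AEs due to the TURBT procedure. It also orders separate tables of TEAEs and of related TEAEs, and a listing of all AEs.

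**The concern.** Safety and dose tolerance is the primary objective, and the TEAE tables are among its main outputs. If the site follows footnote 10, every newly recorded non-serious event after TURBT is by construction one judged related to CPX-POM. From then on the all-cause table adds only related events. If the site follows section 8, the table is all-cause to Follow-up. SAP 9.4 asks for no label and no split at TURBT, so a reader of the report could not tell the two apart.

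Footnote 10 also makes recording depend on attribution. Protocol 8.1.1.6 calls an event related only when there is positive support for a causal link, not merely because a link cannot be ruled out. A doubtful event judged unrelated to both drug and surgery would then have no AE entry in the database for later re-review.

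Other outputs cover this only in part. SAP 9.5, 9.6 and 9.8 summarise laboratory, vital-sign and ECG values at each post-baseline time point. The graded laboratory abnormality table in SAP 9.5, however, stops at the date of last dose, so it does not carry Day 35 findings.

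**Working it through.** The plan gives no figure to reproduce. The check sets the rules side by side and then counts days.

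**1. Events with onset after TURBT, by attribution**

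| Judged due to | Footnote 10 | Protocol 8.1.1.1 and 8.1.1.2 | Protocol 9.5.1 | SAP 9.4 summaries |
|---|---|---|---|---|
| CPX-POM | record | record | TEAE | counted |
| TURBT | recording not needed | record | TEAE | excluded |
| Neither | not recorded | record | TEAE | counted |

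- First row: no conflict. The related-TEAE table, and the secondary objective that rests on it, are nominally the same under either rule.
- Second row: footnote 10 is permissive, so a site that records these events satisfies both texts. SAP 9.4 settles the summaries only. Whether these events must be recorded, and so appear in the SAP listing of all AEs, stays open.
- Third row: a direct contradiction. One text leaves the event out, the other requires it, and both TEAE definitions would count it.

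**2. SAEs.** The first sentence of footnote 10 ends full SAE collection at TURBT, against 8.1.1.2 and 8.1.1.5. The 24-hour reporting duties in 8.1.1.4 and 8.1.1.5 have no relatedness limit and no TURBT cut-off, so in practice they largely protect SAEs.

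**3. Laboratory findings.** Section 8.1.3.7 says "Abnormal laboratory tests that are clinically significant should also be recorded as AEs on the CRF, or as medical history if noted during Screening". It has no relatedness limit, and laboratory tests are scheduled at Day 35. This conflicts with footnote 10 only by inference.

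**4. Time covered.** Inputs: one dose daily on Days 1 to 5 (Protocol 6.1.4), TURBT 2 to 6 h after the fifth dose (footnote 16), Follow-up at Day 35 (Table 1).

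- First dose = 0 h; fifth dose = 4 × 24 = 96 h.
- TURBT = 98 to 102 h = 4.08 to 4.25 d.
- Day 1 to Day 35 = 34 d.
- After TURBT: 34 − 4.25 = 29.75 d to 34 − 4.08 = 29.92 d.
- Share: 29.75/34 = 87.5% to 29.92/34 = 88.0%.

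The permitted visit windows differ. Footnote 1 gives 30 ± 3 d after the last dose (Day 32 to 38); 8.1.1.2 gives 28 ± 5 d (Day 28 to 38).

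- Earliest visit, Day 28: 22.75 to 22.92 of 27 d = 84.3% to 84.9%.
- Latest visit, Day 38: 32.75 to 32.92 of 37 d = 88.5% to 89.0%.

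**5. Weight of one patient.** With 12 patients, one affected patient moves a table row by 1/12 = 8.3 percentage points, provided that patient has no earlier event in the same row.

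**6. Neighbouring inconsistencies**

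- Follow-up: the Synopsis, Protocol 4.1 and SAP 3 require at least 30 days after the last dose (Day 35 or later). A visit at 27 to 29 d meets footnote 1, and one at 23 to 29 d meets 8.1.1.2, but neither meets that minimum.
- Events after consent and before dosing: AEs in footnote 10 and 8.1.1.1, Medical History in 8.1.1.2.

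**The case against.** The best defence is that the cut-off is deliberate. Footnote 10 is the more specific text, and footnote 11 and Protocol 6.2 apply the same cut-off to concomitant medications. What is at issue is mainly non-serious events judged unrelated to the drug, in a descriptive, one-centre study of about 12 patients. SAEs are largely protected and related TEAEs are collected either way. The CPX half-life is typically 2 to 6 hours without accumulation (Protocol 2.1). Taking five half-lives as washout (an assumption), drug is gone by 5 × 6 = 30 h after the last dose, so most of the 30 days is off drug. The causality note required by 8.1.1.6 and the source record of AEs required by 10.2.5 may allow recovery from source.

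Most of this stands, and it limits the size of the point. It does not remove the contradiction: if the cut-off is intended, 8.1.1.1 and 8.1.1.2 are wrong as written and the TEAE tables need a label.

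Four stronger readings are tempting, and the documents do not support them:

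- That some 88% of the safety data is lost. The share is calendar time, and no rate is given for events due to neither cause.
- That a drug event blamed on surgery necessarily vanishes. Footnote 10 only waives the need to record TURBT-related events, and SAP 9.4 keeps them out of the summaries under either rule.
- That SAP 9.4 closes the question for TURBT-related events. It governs summaries, not recording or the listing.
- That pre-dose events cannot reach the TEAE tables. Protocol 9.5.1 works by date, so a Day 1 event before infusion qualifies. SAP 9.4 includes existing AEs that worsened, so a pre-dose AE recorded as such can qualify.

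**Conclusion.** This is an internal contradiction of minor to moderate weight. It is strict for AEs after TURBT judged due to neither CPX-POM nor TURBT. For TURBT-related AEs, recording and listing are unresolved. For SAEs, the wording conflicts but the practical exposure is small.

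The consequence is that the reach of the all-cause TEAE tables is undefined for about 30 of the 34 days to Day 35. The number of events affected cannot be estimated from the documents. The finding rests on the protocol and SAP alone: the CRF and the Study Procedures Manual, to which the protocol refers for SAE reporting procedures, were not available and might state a rule.

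**What to change.** Reconcile footnote 10 with 8.1.1.1, 8.1.1.2 and 8.1.1.5, and state one recording rule for AEs and SAEs from TURBT to Follow-up. Either version works:

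- **Record everything.** Collect all AEs and SAEs through the Day 35 visit, each attributed to CPX-POM, TURBT or neither, so that the SAP 9.4 exclusion acts on recorded data. State whether TURBT counts as a protocol-mandated procedure under 8.1.1.6: the examples there are venipuncture and biopsy, while 4.2 treats TURBT as already scheduled.
- **Keep the cut-off, if deliberate.** Amend 8.1.1.1 and 8.1.1.2 to match, keep SAE collection complete, and label the TEAE tables as all-cause up to TURBT and CPX-POM-related only afterwards.

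If data are already collected, the report should state which rule was followed and label the tables accordingly.

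In the same edit, reconcile the three statements of the follow-up window and the handling of events between consent and first dose. Both are minor.

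Cost: a protocol amendment, notified to the IRB (Protocol 10.1.1). The first version adds some AE entries, although the Day 35 visit already includes an AE assessment. The second adds a table label. Any CRF change is unknown.
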